### **Power Model Analysis**

```
proc mixed data = <data in> alpha = 0.05;
  by parcat1n parcat1 pkday paramn param;
  model lpk = ldose / cl residual ddfm = kr2;
  ods output solutionf = <data out>;
run;
```

### **Power Model Analysis (Between-subject Variability)**

```
proc mixed data = <data in> covtest alpha = 0.05;
  by parcat1n parcat1 pkday paramn param;
  class ldose;
  model lpk = ldose / cl residual ddfm = kr2;
  ods output covparms = <data out>;
run;
(Note: Pooled Geometric CV (%) = 100*(sqrt(exp(estimate)-1)))
```

### **Power Model Analysis (Lack of Fit Test)**

```
proc mixed data = <data in>;
  by parcat1n parcat1 pkday paramn param;
  class dose;
  model lpk = ldose dose / htype = 1 ddfm = kr2;
  ods output tests1 = <data out>;
run;
```

### **ANOVA Model Analysis**

```
proc mixed data = <data in> alpha = 0.05;
  by parcat1n parcat1 pkday paramn param;
  class dose;
  model ldnpk = dose / cl residual ddfm = kr2;
  lsmeans dose / cl pdiff;
  ods output lsmeans = <data out>;
```

```
ods output diffss = <data out>;
ods output tests3 = <data out>;
run;
```

#### 7.5.3.2. Food Effect

A statistical analysis will be conducted to investigate the food effect on the treatment by comparing XX mg AQ280 (fed) treatment to XX mg AQ280 (fasted) treatment for Part A only.

The natural log (ln)-transformed AUC0-tlast, AUCt1-t2, AUC0-∞, and Cmax for AQ280 and AQ282 on profile day 1 will be analyzed using a mixed model. The model will include actual treatment as a fixed effect and subject as a random effect.

For each PK parameter separately, the least squares mean (LSM) for each treatment, difference in LSMSs between the fed and fasted treatments, and corresponding 90% and 95% confidence intervals (CIs) will be calculated; these values will then be back-transformed to give the geometric least square mean (GLSM), ratio of GLSMs, and corresponding 90% and 95% CIs; 2-sided p-value will also be calculated.

Additionally, the pooled estimate (across treatments) of the within-subject coefficient of variation (CV) will be calculated, and residual plots will be produced to assess the adequacy of the model(s) fitted.

Examples of the SAS code that will be used are as follows:

#### Mixed Model Analysis

```
proc mixed data = <data in>;
  by parcat1n parcat1 pkday paramn param;
  class trtan usubjid;
  model lpk = trtan / cl residual ddfm = kr2;
  lsmeans trtan / cl pdiff = control('1') alpha = 0.1;
  lsmeans trtan / cl pdiff = control('1') alpha = 0.05;
  random intercept / subject = usubjid;
  ods output lsmeans = <data out>;
  ods output diffss = <data out>;
  ods output covparms = <data out>;
run;
```

#### 7.6. Pharmacodynamic Assessments

##### 7.6.1. Pharmacodynamic Parameters

In Parts A and B, the relative change from baseline to 48 hours after last dose will be assessed in:

C [REDACTED]

In Part B only, the relative change from baseline to 48 hours after last dose will be assessed in:

C [REDACTED]

C [REDACTED]

I [REDACTED]

The relative change from baseline will be calculated as:

$$\text{relative change} = \frac{\text{value} - \text{baseline}}{\text{baseline}} \times 100$$

where baseline is the last value recorded prior to the first dose.

In Part B only, the absolute change from baseline to 48 hours after last dose will be assessed in:

C [REDACTED]

C [REDACTED]

I [REDACTED]

The absolute change from baseline will be calculated as:

$$\text{absolute change} = \text{value} - \text{baseline}$$

where baseline is the last value recorded prior to the first dose.

Assessments may be obtained from separate blood collections or from scheduled safety clinical chemistry or hematology panels, as applicable.

#### 7.6.2. Presentation of Pharmacodynamic Data

All PD parameters, and their relative and absolute (Part B only) changes from baseline will be listed.

Summary tables and mean figures by treatment and timepoint will be provided for all PD parameters and their relative and absolute (Part B only) changes from baseline.

Values recorded as  $< x$ ,  $\leq x$ ,  $> x$ , or  $\geq x$  will be displayed in the listings as recorded. For the derivation of listing flags, all calculations, and presentation in the figures,  $< x$  and  $\leq x$  values will be set to half of  $x$ , whereas  $> x$  and  $\geq x$  values will be set to  $x$ .

#### 7.6.3. Pharmacodynamic Statistical Methodology

No inferential statistical analyses are planned.

## 7.7. Safety and Tolerability Assessments

### 7.7.1. Adverse Events

All AEs will be coded using the Medical Dictionary for Regulatory Activities (MedDRA) Version 25.0 (or higher if a new version is issued during the study; see the DMP for more details).

A treatment-emergent adverse event (TEAE) will be defined as an AE that starts during or after the first dose, or starts prior to the first dose and increases in severity after the first dose.

A treatment-related TEAE will be defined as a TEAE with a relationship of possibly related or related to the study treatment, as determined by the investigator.

All AEs will be listed. In addition to the data recorded in the database, the listings will include derived onset time and duration. Onset time will be calculated from the time of the last associated dose for TEAEs only. Where the last associated dose is referring to the last dose received prior to the start of a TEAE.

The frequency of subjects with TEAEs and the number of TEAEs will be summarized for the following categories:

- TEAEs (overall, serious, leading to discontinuation, and leading to death) by treatment
- TEAEs by severity and treatment
- Treatment-related TEAEs (overall, serious, leading to discontinuation, and leading to death) by treatment
- Treatment-related TEAEs by severity and treatment

The frequency of subjects will be summarized separately for TEAEs and treatment-related TEAEs by the following:

- System organ class, preferred term, and treatment
- Preferred term and treatment

For the AE data the following rules will apply:

- For the derivation of treatment-emergent status (applicable to all AEs): If the start date/time of an AE is incomplete or missing, an AE will be assumed to not be a TEAE, unless the incomplete start date/time or the end date/time indicates an AE started after the first dose.
- For the derivation of treatment-related status (applicable to TEAEs only): If the study treatment relationship for a TEAE is missing, a TEAE will be assumed to not be a treatment-related TEAE.

- For the derivation of onset time (applicable to TEAEs only): If the start date/time of a TEAE is missing, onset time will not be calculated. If the start date/time of a TEAE is incomplete, where possible, the minimum possible onset time will be calculated and presented in ‘ $\geq$ DD:HH:MM’ format (eg, if the date/time of the last associated dose is 01MAY2019/08:00 and recorded start date/time of a TEAE is 03MAY2019, then the minimum possible onset time will be calculated by assuming a TEAE started at the first hour and minute of 03MAY2019 [03MAY2019/00:00], thus will be presented as onset time  $\geq$ 01:16:00 in the listing). If the start date of a TEAE is the same as the date of the last associated dose but the start time of a TEAE is missing, an onset time will be presented as ‘ $\geq$ 00:00:01’. Any clock changes will be accounted for in the derivation.
- For the derivation of duration (applicable to all AEs): If the end date/time of an AE is missing, duration will not be calculated. If the start or end date/time of an AE is incomplete, where possible, the maximum possible duration will be calculated and presented in ‘ $\leq$ DD:HH:MM’ format (eg, if the start of an AE date/time is 01MAY2019/08:00 and its recorded end date/time is 03MAY2019, then the maximum possible duration will be calculated by assuming an AE ended at the last hour and minute of 03MAY2019 [03MAY2019/23:59], thus will be presented as duration  $\leq$ 02:15:59 in the listing). Any clock changes will be accounted for in the derivation.
- For the calculation of TEAE summary statistics: If the severity of a TEAE is missing, that TEAE will be counted under the ‘missing’ category.
- For the calculation of TEAE summary statistics: If a subject experienced multiple TEAEs with the same preferred term for the same treatment, this will be counted as 1 TEAE for that treatment under the maximum severity recorded.

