3.1.1. Part A (Single Ascending Dose)

Part A will comprise a single-dose, sequential group, escalating-dose design conducted in healthy adult male and female subjects; also incorporating a single-group, 2-period crossover arm investigating the effect of dosing AQ280 with food compared to dosing in the fasting condition. The first dose level administered is planned to be 3 mg AQ280.

A total of approximately 40 subjects are planned to be studied in 5 groups (Groups A1 to A5; with one of the groups including the food effect evaluation). In each group, 6 subjects will receive AQ280 and 2 subjects will receive placebo. The dose will be administered in the fasted state in accordance with the randomization schedule on the morning of Day 1 for all groups, including Period 1 for the food effect evaluation group (see [Section 3.1.1.1](#) for additional food-evaluation group requirements). Each group should contain both male and female subjects, preferably at least 2 subjects of each gender. Additional groups may be added based on the need for more evaluations or groups removed based on data obtained.

The first group in Part A will be divided into 2 cohorts, with each cohort being dosed at least 24 hours apart. The first cohort will comprise 2 subjects, with 1 subject receiving AQ280 and 1 subject receiving placebo. The second cohort will comprise 6 subjects, with 5 subjects receiving AQ280 and 1 subject receiving placebo. The 2 sentinel subjects (first cohort) will be dosed at least 24 hours before the second cohort of 6 subjects. Dosing of subjects in the second cohort will not occur if any of the dose escalation stopping criteria ([Section 3.7](#)) are met by the 2 sentinel subjects. Circumstances under which sentinel dosing may be introduced in other groups are detailed in [Section 3.4.1](#).

There will be a minimum of 9 days between dose escalations for each group.

Potential subjects will be screened to assess their eligibility to enter the study from 2 days up to 5 weeks before the dose of AQ280 or placebo. Each subject will participate in 1 group only and will reside at the study site from Day -1 (the day before dosing) to Day 3 of the treatment period, with dose administration occurring on Day 1. A safety follow-up phone call will be conducted 1 week (± 2 days) after dosing.

Each eligible subject will participate in 1 treatment period only, except for the food effect group, where each subject will participate in 2 treatment periods.

[figure not shown]

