7.3. Safety and Tolerability Assessments

7.3.1. Adverse Events

Adverse event definitions, assignment of severity and causality, and procedures for reporting SAEs are detailed in [Appendix 1](#).

The condition of each subject will be monitored from the time of signing the ICF to final discharge from the study. Subjects will be observed for any signs or symptoms and asked about their condition by open questioning, such as “How have you been feeling since you were last asked?”, at least once each day while resident at the study site and at each study visit. Subjects will also be encouraged to spontaneously report AEs occurring at any other time during the study.

Any AEs and remedial action required will be recorded in the subject’s source data. The nature, time of onset, duration, and severity will be documented, together with an investigator’s (or designee’s) opinion of the relationship to study treatment.

Adverse events recorded during the course of the study will be followed up, where possible, until resolution or until the unresolved AEs are judged by the investigator (or designee) to have stabilized. This will be completed at the investigator’s (or designee’s) discretion.

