## 2. STUDY OBJECTIVES

**Table 1: Objectives and Endpoints**

Objectives	Endpoints
Primary:	

to evaluate the safety and tolerability of single and multiple ascending oral doses of AQ280, and to determine a safe therapeutic range of AQ280 in healthy subjects

	

number of TEAEs per subject

clinically significant abnormalities in vital signs (systolic and diastolic blood pressure, pulse rate, and oral body temperature)

abnormal ECG (QTcF interval of >450 msec for males and >470 msec for females, or change from baseline of >30 msec) measured from Day 1 (postdose) up until 48 hours postdose in Part A and up to the follow-up visit in Part B

clinically significant changes in laboratory evaluations

Objectives	Endpoints

Secondary:
 
 
• to determine the PK of AQ280 after single and multiple oral doses
 
• to determine the PK of the AQ280 main metabolite, AQ282, after single and multiple oral doses
 
• to determine the effect of food on the PK of AQ280 after single oral dose
 
	
Part A (SAD):
 
 
• primary PK parameters derived from plasma concentration-time profile of AQ280: <math>AUC_{0-\infty}</math>, <math>C_{max}</math> (<math>AUC_{0-t_{last}}</math> may be included as a primary PK parameter if <math>AUC_{0-\infty}</math> cannot be calculated)
 
• primary PK parameters derived from plasma concentration-time profile of the AQ280 main metabolite, AQ282: <math>AUC_{0-\infty}</math>, <math>C_{max}</math> (<math>AUC_{0-t_{last}}</math> may be included as a primary PK parameter if <math>AUC_{0-\infty}</math> cannot be calculated)
 
• comparison of the primary PK parameters of AQ280 after single dose administration in the fasted state and in the fed state
 
 
Part B (MAD):
 
 
• primary PK parameters derived from plasma concentration-time profile of AQ280 on Day 1 and Day 7: AR, <math>AUC_t</math>, <math>C_{max}</math>
 
• primary PK parameters derived from plasma concentration-time profile of the AQ280 main metabolite, AQ282, on Day 1 and Day 7: <math>AUC_t</math>, <math>C_{max}</math>
 

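### SAP 7.7.1's default for incomplete AE start times, read literally, drops some events, including some that worsen after dosing, from the primary TEAE count

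*SAP*

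**What the plan says.** The first primary endpoint in SAP Table 1 is the "number of TEAEs per subject".

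SAP 7.7.1 defines a TEAE in two limbs. The first is an AE that begins during or after the first dose. The second is an AE that "starts prior to the first dose and increases in severity after the first dose".

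For an AE whose start is incomplete or missing, the same section sets a default. The AE is "assumed to not be a TEAE, unless the incomplete start date/time or the end date/time indicates an AE started after the first dose". The rule is stated to apply to all AEs.

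Two further rules in 7.7.1 bear on this:

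- Onset time is shown as at least one minute (≥00:00:01) when the start date is "the same as the date of the last associated dose but the start time of a TEAE is missing".
- On counting: "If a subject experienced multiple TEAEs with the same preferred term for the same treatment, this will be counted as 1 TEAE for that treatment".

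All AEs are listed, but every AE summary in 7.7.1 is limited to TEAEs or treatment-related TEAEs. Protocol 7.3.1 says of each AE that "time of onset, duration, and severity will be documented".

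**The concern.** The default runs against the cautious direction for a primary safety endpoint. A record that cannot show postdose onset is treated as though onset were predose, so the rule can only lower the TEAE count. A first-dose-day AE without a clock time is the obvious case. The exception also mentions only onset after the first dose and ignores the worsening limb of the definition. An AE can therefore meet the definition and still be excluded because a clock time with no bearing on the question is blank.

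An excluded event is absent from the primary count and from the tables by severity, relationship, system organ class and preferred term. It is left only in the listing.

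**Working it through.** **Date handling.** The SAP's own worked examples use a dose at 01MAY2019 08:00, and both reproduce:

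- Onset: 03MAY 00:00 − 01MAY 08:00 = 1 day 16 h 0 min, shown as ≥01:16:00.
- Duration: 03MAY 23:59 − 01MAY 08:00 = 2 days 15 h 59 min, shown as ≤02:15:59.

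**The default applied to test records, same dose time.** An incomplete start shows postdose onset only if the earliest start consistent with the record is at or after the dose.

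| Record | Earliest possible start | Result under the default |
|---|---|---|
| First-dose day, no time | 01MAY 00:00 | not a TEAE |
| First-dose day, no time, ended 14:00 that day | 01MAY 00:00 | not a TEAE |
| Start missing, no end | any time from consent | not a TEAE |
| Start missing, ended three days after dose | any time from consent | not a TEAE |
| Month only, month of the dose | 01MAY 00:00 | not a TEAE |
| Day −1, no time, worsens after dose | 30APR 00:00 | not a TEAE |
| Later date (03MAY), no time | 03MAY 00:00 | TEAE |
| First-dose day, 09:00 (complete) | 01MAY 09:00 | TEAE |

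**The end date/time clause.** Onset cannot be later than the end. An end before the dose therefore proves predose onset, but an end after the dose is compatible with onset on either side. The clause can never satisfy this exception. It would do useful work under the opposite default.

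**The worsening limb.** With a time of, say, 14:00 recorded, a Day −1 AE that worsens after dosing is a TEAE by definition. Without that time its start is incomplete, it did not begin after the first dose, and the exception fails. An AE with an unplaceable start that worsens after the first dose meets the definition on either side of the dose, and it too is excluded.

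**Size per lost event.** Each group has 6 active and 2 placebo subjects; the SAP's treatment tables pool placebo over A1–A5 and over B1–B3.

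- Active group: 1/6 = 16.7 percentage points of incidence.
- Part A placebo: 5 × 2 = 10 subjects; 1/10 = 10.0 points.
- Part B placebo: 3 × 2 = 6 subjects; 1/6 = 16.7 points.

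These apply if the event was the subject's only TEAE. The number of TEAEs falls by one unless the subject has another TEAE with the same preferred term under the same treatment.

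**Share of postdose days that are the first-dose day**, to nominal follow-up:

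- Part A: four groups × 8 subjects × 8 days = 256; A3 at the minimum washout 8 × (7 + 8) = 120; 40/376 = 10.6%. With follow-up ±2 days: 40/456 = 8.8% to 40/296 = 13.5%.
- Part B: 24 × 14 = 336; 24/336 = 7.1%. With follow-up ±3 days: 24/408 = 5.9% to 24/264 = 9.1%.

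This is a share of days, not of AEs, and covers only the untimed first-dose-day route. The documents do not say how often start times are missing.

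**The case against.** **The sentence may be unclear rather than exclusionary.** The SAP does not define *indicates*. A programmer might accept an end date after dosing as sufficient. The literal reading also leaves the end clause with nothing to do, which is weak evidence that exclusion was intended. This stands as a point about intent. It does not remove the problem: two programmers could derive different primary counts from the same data, and no reading of *indicates* rescues a Day −1 AE that worsens, because it did not start after the first dose.

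**A reader might infer that the ≥00:00:01 onset rule contradicts the default.** The documents do not support that. In the four single-dose Part A groups the onset rule has nothing to act on, but it still acts on Part B Days 2–7 and on Period 2 in Group A3. It is redundant in some groups. At most it suggests that the authors expected untimed dose-day events to be TEAEs.

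**The worsening conflict depends on how worsening is recorded.** If an increase in severity is entered as a new AE with its own start, this part narrows. The case report form and data management plan are not available, so the condition stands. The other two kinds of event do not depend on it.

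**Other controls limit the harm.** Subjects are resident on Day 1 and questioned at least daily, onset time is recorded, and Protocol Appendix 5 provides for source verification and data queries. Safety analysis is descriptive (SAP 7.7.6), so no test result moves. Protocol 8.5 plans summaries of AEs without a TEAE limit, SAP section 9 declares no change to that, and the table shells cannot be seen. These points bear on frequency and consequence. However, SAP section 1 says the SAP supersedes the protocol's statistical text, and no AE summary described in 7.7.1 would recover an excluded event.

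**Conclusion.** The concern holds on the literal text. The default excludes untimed first-dose-day AEs, AEs with unplaceable starts, and AEs with any incomplete start that worsen after the first dose; the last assumes worsening is kept on the same record. Untimed AEs dated after the first-dose day remain TEAEs.

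The effect is probably small in number but coarse per event: 16.7 points of incidence in an active group, 10.0 in pooled Part A placebo and 16.7 in pooled Part B placebo, where the event was the subject's only TEAE.

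Three stronger conclusions might be drawn, and the documents support none of them:

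- **That the rule favours AQ280.** It applies alike to active and placebo, and nothing shows that missing times differ between them.
- **That it weakens dose escalation.** Under Protocol 3.6 the dose escalation committee reviews all available data, not this derivation.
- **That events vanish from the report.** All AEs are listed.

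The rule should still be corrected, because rarity does not justify a default that can only undercount a primary safety endpoint.

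**What to change.** Replace the treatment-emergent status rule in SAP 7.7.1 with:

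> An AE whose start date or time is incomplete or missing will be treated as a TEAE unless the available start information shows onset before the first dose (with no later increase in severity) or the end date/time is before the first dose. In Group A3, a TEAE that cannot be placed in one period will be counted under each treatment (fasted, fed) that the available dates do not rule out, and once in any overall total.

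Flag all such AEs in the listing. The A3 sentence is needed because SAP Table 2 presents fasted and fed as separate treatments. The new default gives the end date/time a function, agrees with the worsening limb, and lets the ≥00:00:01 rule apply to first and later doses alike. SAP section 1 requires the SAP to be final before any unblinding for analysis, so the change belongs before that point.

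The cost is two sentences and a flag, with some overcounting. Some predose Day 1 AEs without a time will become TEAEs, as will some undated screening-period AEs not shown to have ended before dosing. The latter can arise because "The condition of each subject will be monitored from the time of signing the ICF to final discharge from the study", and Part A screening runs "from 2 days up to 5 weeks before the dose of AQ280 or placebo" (the Part B window is the same). Assuming consent at screening, onset spread evenly to nominal follow-up and no end information, the predose share of wholly undated AEs would be:

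- Part A single-dose groups: 2/(2 + 8) = 20% to 35/(35 + 8) = 81%.
- Part B: 2/(2 + 14) = 12.5% to 35/(35 + 14) = 71%.

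That overcount is real, but the flag lets a reader identify every such event.

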4.4. Subject Withdrawal and Replacement

A subject is free to withdraw from the study at any time. In addition, a subject will be withdrawn if any of the following criteria are met:

- change in compliance with any inclusion/exclusion criterion that is clinically relevant and affects subject safety as determined by the investigator (or designee)
- noncompliance with the study restrictions that might affect subject safety or study assessments/objectives, as considered applicable by the investigator (or designee)
- any clinically relevant sign or symptom that, in the opinion of the investigator (or designee), warrants subject withdrawal.

If a subject is withdrawn from dosing, the sponsor will be notified and the date and reason(s) for the withdrawal will be documented in the subject's electronic case report form (eCRF). If a subject is withdrawn from the study, efforts will be made to perform all follow-up assessments, if possible ([Appendix 6](#)). Other applicable safety-related procedures may be performed at the investigator's (or designee's) and/or sponsor's discretion. If the subject is in-house, these procedures should be performed before the subject is discharged from the

clinic. The investigator (or designee) may also request that the subject return for an additional follow-up phone call or visit. All withdrawn subjects will be followed until resolution of all their AEs or until the unresolved AEs are judged by the investigator (or designee) to have stabilized.

Subjects who are withdrawn for reasons not related to study treatment may be replaced following discussion between the investigator and the sponsor. Subjects withdrawn as a result of AEs thought to be related to the study treatment will generally not be replaced.

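### A TEAE with no causality entry is set to not treatment-related (SAP 7.7.1) and drops out of all four treatment-related summaries with nothing to show that the judgement is missing

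*SAP*

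**What the plan says.** SAP 7.7.1 defines a treatment-related TEAE as one with "a relationship of possibly related or related to the study treatment, as determined by the investigator". For a blank relationship it adds: "If the study treatment relationship for a TEAE is missing, a TEAE will be assumed to not be a treatment-related TEAE".

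Four outputs use this status:

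- the overview: "Treatment-related TEAEs (overall, serious, leading to discontinuation, and leading to death) by treatment"
- the severity table: "Treatment-related TEAEs by severity and treatment"
- two further tables, one by system organ class and preferred term and one by preferred term alone, introduced by "The frequency of subjects will be summarized separately for TEAEs and treatment-related TEAEs by the following".

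Missing severity is handled differently in the same section: "If the severity of a TEAE is missing, that TEAE will be counted under the" missing category. SAP 7.1.2 sets the general default for categorical data, which is no imputation and a missing category, but allows exceptions where the SAP specifically says so. On listings, SAP 7.7.1 says: "All AEs will be listed".

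**The concern.** Protocol Appendix 1 gives the investigator four causality categories, and none of them means unknown. A blank field therefore records that no assessment was entered. It does not record that the event was judged unrelated. The SAP rule turns that absence into a negative answer, and the treatment-related tables then look the same as they would had the investigator actually ruled the drug out.

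The primary objective of this first-in-human trial is safety and tolerability, and each dose level has 6 AQ280 subjects. A reader who turns to the treatment-related tables to see how a dose was tolerated cannot tell a true zero from a zero that rests on an unmade judgement. The SAP gives no reason for treating causality less openly than severity.

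**Working it through.** **Step 1: follow one event through the rules.** Take a TEAE with severity recorded and relationship blank.

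| Output | Is the event there? | Is the gap visible? |
|---|---|---|
| All-TEAE overview, severity, SOC/PT and PT tables | yes | not applicable |
| AE listing | yes | yes, on reading the line |
| Treatment-related overview | no | no |
| Treatment-related by severity | no | no |
| Treatment-related by SOC and PT | no | no |
| Treatment-related by PT | no | no |
| Primary endpoint, TEAEs per subject | yes | not applicable |

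Now reverse the gap, with relationship recorded as related and severity blank. The event appears in the treatment-related severity table under a missing category. So the section hides one kind of gap and shows the other.

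**Step 2: size in one table column.** Inputs: 6 AQ280 and 2 placebo subjects per group, 5 groups in Part A and 3 in Part B (SAP 3.1.1 and 3.1.2). SAP Tables 2 and 4 give each AQ280 dose its own treatment label and pool placebo within each part.

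Suppose one AQ280 subject has a single candidate related TEAE and its relationship is blank.

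- As planned: 0/6 = 0%.
- If the event were in fact related: 1/6 = 16.7%.
- Difference: 16.7 percentage points.

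For scale only, exact (Clopper-Pearson) 95% intervals are 0 to 45.9% for 0/6, with upper limit 1 − 0.025^(1/6) = 0.459, and 0.4 to 64.1% for 1/6. The SAP plans no such intervals.

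Pooled over dose groups, the same event matters less:

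- Part A, 5 × 6 = 30 subjects: 0/30 = 0% against 1/30 = 3.3%.
- Part B, 3 × 6 = 18 subjects: 0/18 = 0% against 1/18 = 5.6%.

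The rule acts on placebo in the same way. In Part A, with 5 × 2 = 10 placebo subjects, the contrast is 0/10 = 0% against 1/10 = 10%.

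**Step 3: how likely is it to bite?** The documents give no rate of missing causality. Assume a chance q of 1% to 10% per event, independent between events. The probability that at least one of m truly related TEAEs is left out is 1 − (1 − q)^m.

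| m | q = 1% | q = 10% |
|---|---|---|
| 5 | 4.9% | 41.0% |
| 10 | 9.6% | 65.1% |
| 20 | 18.2% | 87.8% |

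These figures depend wholly on the assumed q and m. With q = 0 the probability is 0. A subject count also stays the same if that subject has another related TEAE in the same table row.

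**The case against.** The strongest reply is that the gap should hardly ever arise and does little when it does. Protocol 7.3.1 requires an investigator's opinion on relationship for AEs. The SAE form in Appendix 1 collects that opinion, and reporting is due within 24 hours. Appendix 5 requires source data verification, resolution of queries and an investigator's signature on the eCRF. The primary AE endpoint does not use causality, and SAP 7.7.6 plans no inference on safety. The rule applies equally to AQ280 and placebo, so it is not biased between arms by construction. Counting a missing relationship as related would also be an imputation. All of this stands. It limits how often the rule matters and how much, but it does not explain why a residual gap should be invisible. The SAP foresaw the gap by writing a rule for it, and SAP 7.1.1 names incomplete data entry and unanswered queries as recognised risks.

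A reader might infer more than the documents support:

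- **That the rule mainly affects subjects who withdraw or are lost.** Causality is the investigator's judgement and does not need the subject present. The data gaps named in SAP 7.1.1 concern missed visits, supply, data entry, verification and queries. Nothing links missing causality to early stopping.
- **That the rule conflicts with subject replacement.** Protocol 4.4 says "Subjects withdrawn as a result of AEs thought to be related to the study treatment will generally not be replaced". That decision is taken during the study on a judgement already made, not from this derivation.
- **That the SAP contradicts itself.** SAP 7.1.2 permits stated exceptions, and this is one. The treatment of severity is a contrast, not a conflict.
- **That safety decisions are affected.** The stopping criteria in Protocol 3.7 and the dose escalation committee's review in Protocol 3.6 work from in-study data, not from this flag.
- **That the related count is certainly too low.** An unassessed event may truly be unrelated. Hence up to 1/6, not 1/6.

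**Conclusion.** The point holds as a minor one about transparency. Any TEAE still lacking a causality entry at analysis is left out of all four treatment-related summaries, and no row, footnote or sensitivity table is specified to say so. At worst, one such event makes a 6-subject AQ280 group read 0/6 instead of up to 1/6, a difference of 16.7 percentage points in that column. This assumes that it is the subject's only candidate related TEAE. The effect is nil if causality is complete, which the protocol's procedures aim for and which the documents give no figure to contradict.

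**What to change.** Replace the SAP 7.7.1 bullet with wording along these lines:

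> TEAEs whose relationship is still missing after query resolution will be shown in a separate row, labelled relationship missing, in the treatment-related summaries, with a footnote. They will not be classed as not related.

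An acceptable alternative is to count them as treatment-related, with a footnote giving their number. The separate row is the more neutral choice because it assigns no judgement in either direction, and it matches what the section already does for severity.

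The cost is one SAP sentence, one line of derivation code and a row or footnote in the table shells. Under the alternative, the related-TEAE count may rise slightly in either arm. If no relationship is missing at database lock, the reported counts do not change.
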